6.1.2 Comparator Treatment

Arthroscopic rotator cuff repair (ARCR) alone.

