7.6 ENROLLMENT

Every subject that has signed consent, met inclusion/exclusion criteria, and received either ARCR augmented with REGENETEN or ARCR alone will be considered enrolled in the study.

In the event that a subject has a sequential bilateral ARCR augmented with REGENETEN or ARCR alone, both shoulders treated after informed consent can be enrolled in the study.

A subject that has been randomized into the ARCR augmented with REGENETEN arm and with a diagnosis of a recurrent large or massive tear will not be enrolled into the revision repair subject group. However subjects that were randomized into the ARCR alone arm can be enrolled into the revision repair subject group in case of recurrent large or massive tears.

Subjects that provided informed consent but do not receive the study treatment for any reason will be considered as screen failure.

CONFIDENTIAL AND PROPRIETARY

Study Protocol	Smith-Nephew
A Prospective, Multi-center, Randomized Controlled	Number:
Study to Evaluate the Safety and Efficacy of ARCR	REGENETEN.2020.01
augmented with REGENETEN™ Bioinductive Implant	Version: 2, 08 Dec 2021
System in Full-thickness Tears (large or massive) Repair versus ARCR alone	Page: 42 of 134

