7.8 WITHDRAWAL

7.8.1 Withdrawal from Treatment

Subjects may be withdrawn from having the study device implanted at a date close to surgery or during surgery for the following reasons:

- At the discretion of the Investigator due to:
 - A change in treatment being clinically warranted
 - An adverse event
 - Any other significant reason identified by the Investigator.

If at any point during the study, the study device needs to be revised for any reason intraoperative data from the reoperation will be collected according to the Reoperation Case Report Form (CRF).

Reoperation cases will not be enrolled into the revision repair subject group if the subjects has been randomized previously into the ARCR augmented with REGENETEN arm. However subjects that have been randomized into the ARCR alone arm can be enrolled into the Revision Repair subject group.

CONFIDENTIAL AND PROPRIETARY

Study Protocol	Smith-Nephew
A Prospective, Multi-center, Randomized Controlled	Number:
Study to Evaluate the Safety and Efficacy of ARCR	REGENETEN.2020.01
augmented with REGENETEN™ Bioinductive Implant	Version: 2, 08 Dec 2021
System in Full-thickness Tears (large or massive) Repair versus ARCR alone	Page: 43 of 134

Following reoperation subjects shall continue to have follow-up visits in order to monitor the subject's health status only. Potential data following the reoperation will not be included as study data but presented separately as safety data.

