9.1.11.1.2 Recording Concomitant Medication in the eCRF

Only medication related to the study treatment and therapies used to treat an adverse event related to study device and/or study procedure and device deficiency will be recorded in the eCRF according to the eCRF Completion Guidelines.

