10.2 ANALYSIS POPULATIONS

The following study populations and analysis sets will be defined.

- Full analysis set (FAS): following the Intention to Treat principle including all randomized patients who were recruited into the study and attended at least one post-surgery assessment. This analysis population includes all randomized patients in the groups to which they were randomly assigned, regardless of their adherence with the entry criteria, regardless of the treatment they actually received, and regardless of subsequent withdrawal from treatment or deviation from the protocol.
- Per protocol set (PP): including all patients in the full analysis set who have no significant protocol deviations and met the inclusion/exclusion criteria.
- Safety analysis set (SAF): including all patients who have received the study device.

CONFIDENTIAL AND PROPRIETARY

Study Protocol	Smith-Nephew
A Prospective, Multi-center, Randomized Controlled	Number:
Study to Evaluate the Safety and Efficacy of ARCR	REGENETEN.2020.01
augmented with REGENETEN™ Bioinductive Implant	Version: 2.0, 08 Dec
System in Full-thickness Tears (large or massive) Repair	2021
	Page: 71 of 134

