10.5 SAFETY ANALYSES

All safety endpoints will be summarized using the safety population.

Adverse Events

The number of subjects reporting: adverse events, serious adverse events, adverse device effects, serious adverse device effects, and unanticipated serious device effects will be summarized. In addition, for each adverse event, the following will be summarized: severity, the relationship to investigational device use, outcome and duration of the resolved adverse events and the duration of the adverse events at trial discontinuation.

Device deficiencies

The number of device deficiencies and the number of patients reporting a device deficiency will be summarized as well as a summary of device deficiencies with the potential to cause SADE.

Additional summaries of safety endpoints, if applicable, will be described in the SAP.

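### The safety set is defined by receipt of the study device, so as written it drops the ARCR-alone arm from every adverse event table, although safety versus ARCR alone is a secondary objective

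*Combined protocol and SAP*

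**What the plan says.** Section 10.2 gives the only definition of the safety population: "Safety analysis set (SAF): including all patients who have received the study device". Section 10.5 then states: "All safety endpoints will be summarized using the safety population". The summaries it lists are counts of patients with AEs, serious AEs and device effects, followed by severity, relatedness, outcome and duration. It does not say that these are shown by arm. It closes with "Additional summaries of safety endpoints, if applicable, will be described in the SAP", and section 10 describes itself as a short account of analyses that the SAP will set out.

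Section 6.1.2 gives the comparator in full as "Arthroscopic rotator cuff repair (ARCR) alone". Section 5.2 sets the secondary objective as safety and efficacy against that comparator. Section 8.3.4 collects AEs from enrolment, section 7.6 counts ARCR-alone patients as enrolled, and the AE definition in section 12.1.1 covers events related to the comparator.

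**The concern.** Sections 10.2 and 10.5 together decide who appears in the AE tables. If *study device* means the REGENETEN implant, the control arm is absent, and its AE data are collected but never summarised.

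That matters because the complications in section 4.4.4 belong to the operation: infection, nerve damage, persistent stiffness and tissue inflammation can follow any such repair. An AE rate in implant recipients alone cannot separate what the implant adds from what the surgery causes.

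There is also a selection problem. The route the protocol describes for an ARCR-alone patient to receive the implant is a recurrent large or massive tear followed by entry to the revision group (sections 7.6 and 7.8.1). Controls who entered the safety set that way would all be failed repairs, which is not a fair comparison group.

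**Working it through.** The plan states no size for the safety set and no AE rate, so there is no figure to reproduce. The check has three parts: wording, head count and precision.

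**1. What *study device* means in the protocol**

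- Section 7.8.1 treats it as something implanted: "Subjects may be withdrawn from having the study device implanted at a date close to surgery".
- Section 9.1.11.1.2 sets it apart from the procedure: "an adverse event related to study device and/or study procedure and device deficiency".
- Where section 7.6 needs a term for either arm, it uses a broader one: "Subjects that provided informed consent but do not receive the study treatment for any reason will be considered as screen failure".
- The full analysis set, defined just above the safety set in section 10.2, refers to treatment received and not to a device.
- The only investigational product described in section 6.1.1 is REGENETEN. Section 6.1.2 names no device for the comparator.

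The natural reading is therefore that receiving the study device means receiving REGENETEN. Section 10.4.3 refers safety in the at-risk and revision groups to the secondary endpoint analysis, but section 10.4.2 contains no AE analysis, so it does not bring the controls back. By-arm presentation is explicit in section 10.4.2 for the patient-reported scores, opioid use, operative time and sling type. It is not stated for AEs.

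**2. Head count on the literal reading**

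Inputs: 130 and 130 randomised (section 11); up to 40 revision patients, all given REGENETEN (section 8.2.1); control retear rate 30% (section 11).

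- Patients in the set: 130 + 40 = up to 170.
- Share that is non-randomised: 40/170 = 23.5%.
- Controls able to enter through the revision group: 0 to 40 of 130, or 0 to 30.8%.
- Controls left out: 130/130 = 100% down to 90/130 = 69.2%.
- Control retears expected by 6 months: 0.30 × 130 = 39. Entry also needs a reoperation and a tear of at least 3 cm, so the upper end of 40 is a bound and not a forecast.

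These counts ignore an implant given by deviation or in a second enrolled shoulder.

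**3. What the comparison would deliver with both arms in the set**

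Half-width of the 95% interval for a difference in proportions, with the same rate p in both arms: 1.96 × √(2p(1−p)/n). The AE rates are assumptions. The n = 104 column assumes that 20% of each arm is missing (0.80 × 130).

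| AE rate p | n = 130 per arm | n = 104 per arm |
|---|---|---|
| 2% | 3.4 points | 3.8 points |
| 5% | 5.3 points | 5.9 points |
| 10% | 7.3 points | 8.2 points |
| 20% | 9.7 points | 10.9 points |

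For example, at p = 5% and n = 130: 1.96 × √(0.095/130) = 1.96 × 0.0270 = 0.053. With the set as worded, the randomised part is 130 against 0, apart from any controls later implanted, and this estimate cannot be formed.

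**The case against.** The strongest reply is that the sponsor plainly means to tabulate both arms. The objective is comparative, AEs are collected in both arms, and the AE definition covers the comparator. The protocol's terms are also loose: section 7.8.1 moves from revising the study device straight to reoperation rules that include ARCR-alone patients, and section 9.1.11.1.2 separates device from procedure for attributing AEs, not for defining arms. Section 10 is a summary, and the SAP is to be finalised before database lock. On intent this is right, and it makes the literal reading less certain. It does not change the definition as written. Section 10.5 leaves additional summaries to the SAP, not the population, and loose terms in a rule that can remove a whole arm are themselves a reason to rewrite it.

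A second reply is that much safety-relevant comparison does not use this set. Retear is the primary endpoint by arm. Pain and the Constant-Murley score, which includes range of motion, are compared between arms. Reoperations and unscheduled visits are planned against ARCR alone (section 8.3.3). That stands: the gap is in AE, serious AE and related tabulations, not in all evidence bearing on harm.

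It is also fair to say that 40 controls entering the revision group is extreme, since Sugaya Type IV denotes a small tear and many retears would fall short of 3 cm. The interval widths rest on assumed rates and show what is forgone; they do not measure the wording defect.

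**Conclusion.** The point holds. Followed as written, sections 10.2 and 10.5 leave 69% to 100% of the control arm out of every AE summary, most likely near the upper end, and the AE part of the secondary safety objective cannot be met. The conclusion assumes that *study device* means REGENETEN, which the protocol's own usage supports, and that no later text redefines the set. The primary analysis, the error rate and the sample size are unaffected, and no data are lost. It should be corrected before database lock, but it is not a threat to the trial's main result.

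**What to change.** In section 10.2, and in the SAP, define the safety set as all patients who received study treatment, either ARCR augmented with REGENETEN or ARCR alone, analysed by the treatment received at the index operation.

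In section 10.5:

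- Show all AE and serious AE categories, including stiffness, for randomised patients in two columns, one per arm.
- Show the revision group in its own column.
- Show events after a reoperation separately. This follows section 7.8.1: "Potential data following the reoperation will not be included as study data but presented separately as safety data". An ARCR-alone patient who joins the revision group then counts under ARCR alone only up to that operation.
- Keep device-deficiency tables for patients in whom the device was used or attempted.
- Optionally, add the difference in proportions with a 95% interval for any AE and any serious AE, as description without tests. If treatment received differs from the randomised arm for anyone, list the patient and repeat these two rows by randomised arm.

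The SAP should also say how events are assigned when both shoulders of one patient are enrolled (sections 7.4 and 7.6), because that patient may receive both treatments.

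The cost is one sentence in section 10.2, a table layout in section 10.5 and a wider AE table. AEs are already collected in both arms.

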10.3 BASELINE DATA

Demographic and medical variables at baseline (including but not limited to, age, gender, race, job type (laborer/sedentary), medical history, medication history, and disease diagnosis) will be used to describe subjects and summarize subject information. Summary statistics will be given based on the nature of variables (continuous or categorical variables). Job role will be analyzed by Sedentary, Light, Medium and Heavy (heavy and very heavy) according to the US Social Security Administrations classification of labor by physical exertion requirements.

10.4 EFFICACY ANALYSIS

10.4.1 Analysis of Primary Endpoint

A binary variable will be defined based on whether each patient has a Sugaya score of Type IV or V retear/recurrence. This variable will be used to present the number of retears at the 6 month post-operative visit, together with a percentage and 95% confidence interval for a single proportion (calculated using the Clopper-Pearson Exact method).

To test whether ARCR augmented with REGENETEN is superior to ARCR alone, the null hypothesis is that the retear rate of the ARCR augmented with REGENETEN group is not better than, or the same as, the retear rate of the ARCR alone group (standard of care)::

$$H_0: \mu - \mu_0 \ge 0$$

$$H_1$$
: $\mu - \mu_0 < 0$

In the stated hypothesis, μ represents the rate of retear for those patients which received REGENETEN and μ_0 represents the rate of retear for the standard of care group. A binary variable of success/failure will be created to fit a logistic model adjusting for differences in baseline characteristics.

CONFIDENTIAL AND PROPRIETARY

Study Protocol	Smith-Nephew
A Prospective, Multi-center, Randomized Controlled	Number:
Study to Evaluate the Safety and Efficacy of ARCR	REGENETEN.2020.01
augmented with REGENETEN™ Bioinductive Implant	Version: 2.0, 08 Dec
System in Full-thickness Tears (large or massive) Repair	2021
versus ARCR alone	Page: 72 of 134

As a further analysis of the primary endpoint, the time taken for retear to occur will be assessed as a survival endpoint for both treatment groups in order to compare the trend of incidence of retear over time.

Analysis will be carried out using the FAS and PP population.

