8.2.2 Blinding

This is not a blinded study.

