8.3 STUDY ENDPOINTS

8.3.1 Primary Endpoint

The primary study endpoint is the cumulative 6 months retear rate after full-thickness ARCR augmented with REGENETEN versus ARCR alone. Failure is defined as Sugaya Type IV or V retear/recurrence (full-thickness discontinuity seen on both coronal and oblique sagittal MRI images).

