8.3.2 Secondary Endpoints

The secondary study endpoints are:

- The cumulative 3, 12, and 24 months retear rate after full-thickness ARCR augmented with REGENETEN (confirmed on MRI) versus ARCR alone;
- Overall performance of full-thickness ARCR augmented with REGENETEN versus ARCR alone at Baseline and at 3, 6, 12 and 24 months assessed by:
 - Oxford Shoulder Score (OSS),
 - Western Ontario Rotator Cuff (WORC)/Chinese version WORC (C-WORC) Index,
 - Constant-Murley Score,
 - Subjective shoulder value (SSV),
 - o EuroQol 5 Dimension 5 Level (EQ-5D-5L) Score,
 - Patient satisfaction Questionnaire,
 - Pain, Visual analog scale (VAS) Score (additionally at baseline, 2 weeks, 6 weeks, 3 months and 6 months);
- MRI Tendon Findings in ARCR augmented with REGENETEN versus ARCR alone postoperatively at Baseline, 3, 6, 12 and 24 months including:
 - Sugaya score,

CONFIDENTIAL AND PROPRIETARY

Study Protocol	Smith-Nephew
A Prospective, Multi-center, Randomized Controlled	Number:
Study to Evaluate the Safety and Efficacy of ARCR	REGENETEN.2020.01
augmented with REGENETEN™ Bioinductive Implant	Version: 2, 08 Dec 2021
System in Full-thickness Tears (large or massive) Repair versus ARCR alone	Page: 49 of 134

- Goutallier grading,
- o Total tendon thickness, tendon length,
- Size of retear (anteroposterior [AP]/mediolateral [ML]),
- Shape of retear;
- Outcome of Return to Work Questionnaire in ARCR augmented with REGENETEN versus ARCR alone (additionally at 2 and 6 weeks);
- Cumulative duration of opioid use in ARCR augmented with REGENETEN versus ARCR alone at 2 weeks postoperatively;
- Total operative time in ARCR augmented with REGENETEN versus ARCR alone;
- Sling type and mobilization time in ARCR augmented with REGENETEN versus ARCR alone.

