9.1.4 Postoperative Follow-up Visit 3 (2 Weeks [14 days ± 5 days])

- Query subject regarding any changes in general health and the use of concomitant medications. If any AEs, ADEs or DDs are observed or reported, they must be recorded as instructed in Section 12 – Adverse Events and Device Deficiencies.
- 2. Have the subject complete VAS pain score.
- 3. Have the subject complete the Return to Work Questionnaire (if appropriate).

CONFIDENTIAL AND PROPRIETARY

Study Protocol	Smith-Nephew
A Prospective, Multi-center, Randomized Controlled	Number:
Study to Evaluate the Safety and Efficacy of ARCR	REGENETEN.2020.01
augmented with REGENETEN™ Bioinductive Implant	Version: 2.0, 08 Dec
System in Full-thickness Tears (large or massive) Repair	2021
versus ARCR alone	Page: 57 of 134

- 4. Collect daily Opioid Use documentation from subject and enter into eCRF.
- 5. If any Reoperation occurred complete reoperation CRF.
- 6. Complete End of Study/exit information (if appropriate).
- 7. Instruct the subject on follow-up procedures, including returning the treatment facility for follow-up at Visit 4 at 42 (± 7) days.

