9.2.12 Imaging Examinations

Upper extremity MRIs for study participants will be collected at Baseline, at 3, 6, 12 and 24 months. The Baseline (pre-operative) MRI follows standard of care imaging and will not follow the study MRI Image Acquisition Protocol. The Baseline MRI must occur within 12 months of enrollment into this study. MRI at 3, 6, 12 and 24 months post-surgery will be collected per Image Acquisition Protocol. All diagnostic images collected by the site will be modified in order to protect subject's identity and provided to an external reviewer as detailed in the Image Transfer

CONFIDENTIAL AND PROPRIETARY

Study Protocol	Smith-Nephew
A Prospective, Multi-center, Randomized Controlled	Number: REGENETEN.2020.01
Study to Evaluate the Safety and Efficacy of ARCR augmented with REGENETEN™ Bioinductive Implant	Version: 2.0, 08 Dec
System in Full-thickness Tears (large or massive) Repair	2021
versus ARCR alone	Page: 68 of 134

Protocol. The independent reviewer will be a certified radiologist selected by the Sponsor based on experience in orthopaedic imaging. The following reviewer assessments will be performed for all MRIs collected post-OP throughout the study (for endpoint analysis):

- Sugaya score
- Goutallier grading
- Total tendon thickness, tendon length
- Size of retear (anteroposterior [AP]/mediolateral [ML])
- Shape of retear

All MRI assessments are detailed in the Image Review Charter. All imaging data will be stored in electronic Digital Imaging and Communications in Medicine (DICOM) format at the site until they are no longer needed in case further evaluation by an independent centralized reviewer is requested by NMPA, PMDA, MHRA, EMA, TGA, Medsafe, HealthCanada, or FDA.

The specific imaging evaluation requirements will be provided in a separate document to radiologists.

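### The retear endpoints are cumulative, but section 10.4 counts retears at the visit, and no rule carries an earlier Sugaya IV/V forward

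*Combined protocol and SAP*

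**What the plan says.** **Endpoint sections.** Section 8.3.1: "The primary study endpoint is the cumulative 6 months retear rate after full-thickness ARCR augmented with REGENETEN versus ARCR alone". Failure means Sugaya Type IV or V on MRI. Section 8.3.2 lists "The cumulative 3, 12, and 24 months retear rate after full-thickness ARCR augmented with REGENETEN". The synopsis, section 5.1 and section 8.4.3 also call the primary endpoint cumulative.

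**Analysis sections.** Section 10.4.1 defines a binary variable for Sugaya IV/V without a time window, then says: "This variable will be used to present the number of retears at the 6 month post-operative visit", with a percentage and a Clopper-Pearson interval. A later sentence creates a success/failure variable for a logistic model and gives no time window either. A time-to-retear analysis follows as a further analysis. Section 10.4.2 handles 3, 12 and 24 months in the same way as the primary endpoint.

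**Reoperation.** Section 7.8.1: "Potential data following the reoperation will not be included as study data but presented separately as safety data". Reoperations are recorded from the 2-week visit (section 9.1.4): "If any Reoperation occurred complete reoperation CRF".

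**Imaging.** MRIs are scheduled at baseline and at 3, 6, 12 and 24 months. Under section 9.2.12, "reviewer assessments will be performed for all MRIs collected post-OP throughout the study (for endpoint analysis".

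**Context.** Section 8.2.2: "This is not a blinded study". Section 7.6 states that, after a recurrent large or massive tear, "subjects that were randomized into the ARCR alone arm can be enrolled into the revision repair subject group"; device-arm subjects cannot enter it. Section 10 calls itself brief and leaves detail to an SAP due before database lock. The supplied text contains no separate SAP.

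**The concern.** A cumulative rate counts every subject who has retorn by a given time. A count at a visit covers only those with a qualifying finding at that visit. The two differ whenever an early failure is no longer observable, or no longer graded as a failure, at the later visit.

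Two routes produce that difference here:

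1. A IV/V at 3 months is reoperated before the 6-month MRI. Section 7.8.1 then leaves the subject without a usable 6-month image.
2. A IV/V at 3 months is graded III at 6 months.

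In both routes a failure already on record is missing from a literal 6-month count. What is at stake is the primary outcome of an open-label trial. The interim look in section 11 uses the same endpoint, with options to stop for efficacy or futility or to enlarge the trial.

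**Working it through.** **Step 1: set the rules side by side for a subject with IV/V on the 3-month MRI.**

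| Course after the 3-month MRI | Cumulative endpoint (8.3.1) | Literal visit count (10.4.1 with 7.8.1) |
|---|---|---|
| Reoperated before the 6-month MRI | Failure | No usable 6-month result |
| Graded III at 6 months | Failure | Not counted as a retear |
| Graded IV/V at 6 months | Failure | Failure |

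The 3-month MRI window is 91 − 15 = 76 to 91 + 15 = 106 days. The 6-month window ends at 182 + 30 = 212 days. The first two rows can therefore occur within the schedule.

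**Step 2: reproduce the planned size.** Inputs from sections 10.1 and 11: 30% vs 15%, 80% power, two-sided 5%. The pooled two-proportion formula gives 121 per arm, 242 in total. One O'Brien-Fleming efficacy look at half the information multiplies this by 1.004, to about 243. A non-binding O'Brien-Fleming futility bound as well makes the factor 1.056, about 255, or 256 with equal arms. The planned 260 is close to that last figure, but the documents do not state the futility boundary. The point does not depend on it.

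**Step 3: illustrate route 1 with affected subjects dropped.** Let s be the share of an arm's cumulative retears lost before the 6-month result. The documents give no value, so every s below is an assumption. With true rate p and 130 per arm (39 expected control retears, 19.5 device):

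- remaining n = 130(1 − ps)
- observed rate = p(1 − s)/(1 − ps)
- observed odds = p(1 − s)/(1 − p)
- power = Φ[(difference − 1.96 × SE pooled)/SE unpooled], fixed design

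For s = 0: pooled rate 0.225, SE pooled 0.0518, SE unpooled 0.0510, so power = Φ[(0.15 − 1.96 × 0.0518)/0.0510] = 82.9%.

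| s control / s device | Observed rates | Difference (points) | Odds ratio | Power |
|---|---|---|---|---|
| 0 / 0 | 30.0% vs 15.0% | 15.0 | 0.412 | 82.9% |
| 5% / 5% | 28.9% (n 128.1) vs 14.4% (n 129.0) | 14.6 | 0.412 | 81.4% |
| 10% / 10% | 27.8% (n 126.1) vs 13.7% (n 128.1) | 14.1 | 0.412 | 79.7% |
| 10% / 5% | 27.8% vs 14.4% | 13.5 | 0.435 | 75.5% |
| 5% / 10% | 28.9% vs 13.7% | 15.2 | 0.390 | 84.9% |

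With equal s the factor (1 − s) cancels from the odds ratio, which stays at (0.15/0.85)/(0.30/0.70) = 0.412.

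**Step 4: route 2.** Here the subject stays in the denominator as a non-failure, so the rate is p(1 − s). With s = 5% in both arms: 28.5% vs 14.25%, a difference of 14.25 points and power 80.4%. The odds ratio is (0.1425/0.8575)/(0.285/0.715) = 0.417, so in this route even equal loss moves it slightly.

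**Step 5: under the corrected rule.** If every IV/V seen by 6 months counts, the rates return to 30% vs 15%, fixed-design power returns to 82.9%, and the planned size is unchanged.

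**The case against.** The case for reading the plan as cumulative is good. The endpoint is called cumulative in every section that defines it. The binary variable in 10.4.1 carries no visit limit. All post-operative MRIs are read for endpoint analysis. Section 7.8.1 excludes only what follows a reoperation, so an earlier 3-month MRI stays study data. Section 10.2 keeps these subjects in the FAS, and the time-to-retear analysis can use early events. A derivation rule is also ordinary SAP content. All of this stands. It makes the point an inconsistency to align, but it does not supply the missing carry-forward sentence, and the visit wording remains.

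Three stronger readings are tempting and not supported:

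- **That the primary test drops these failures.** The visit wording governs the descriptive count and its interval. The logistic-model sentence gives no time window, so loss from the model is possible but not stated.
- **That loss will be unequal in a known direction because only control subjects may enter the revision group.** Sections 7.6 and 7.8.1 restrict entry to that group, not reoperation itself, and nothing links entry to reoperation before the 6-month MRI. Equal loss is not assured, but the direction is unknown.
- **That a reoperation for retear before any IV/V study MRI is part of the same contradiction.** It can happen, since reoperations are recorded from 2 weeks and the first scheduled post-operative MRI is at day 76 at the earliest. But it lies outside an MRI-defined endpoint on any reading. It is a question of endpoint scope.

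On timing, section 11 sends the interim details to the SAP, which suggests that some SAP text will exist by then. The only stated deadline is database lock.

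**Conclusion.** The inconsistency is real and should be fixed. Followed as written, sections 10.4.1, 10.4.2 and 7.8.1 can leave a failure already recorded out of the count for a cumulative endpoint. Whether the logistic model is affected cannot be determined from the text.

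The size is unknown. The figures rest on assumed loss shares, the design rates, 130 per arm and a fixed-design pooled formula, whereas the plan is group sequential. Under those assumptions a small equal loss costs 1.5 to 3.2 power points when subjects are dropped. Unequal loss matters more, because it shifts the estimate: more loss in the control arm works against the device, more in the device arm works for it. The point at which power crosses 80% should not be read as a property of this trial; Fisher's exact test at 130 per arm gives 79.7% with no loss at all.

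**What to change.** - **Section 10.4.1:** define the failure variable, for both the count and the logistic model, as Sugaya IV/V on any post-operative study MRI up to and including the 6-month window. Keep these subjects in the FAS as failures.
- **Section 10.4.2:** apply the same rule at 3, 12 and 24 months.
- **Section 7.8.1:** state that excluding data after a reoperation does not remove a failure already recorded.
- **Timing:** fix the rule before the interim analysis.
- **Sensitivity analyses:** keep the visit-only count. Separately, count a reoperation for retear without a prior IV/V study MRI as a failure in a pre-specified sensitivity analysis only.

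**Cost.** No new data are needed: the 3-month MRI, the central read and the reoperation form already exist. The derivation rule and sensitivity analyses can go in the SAP. Changing the wording of sections 7.8.1 and 10.4 is a protocol amendment and needs the approvals in section 15. One small downside is that a IV at 3 months graded III at 6 months counts as a failure; the visit-only analysis shows how much this matters.
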